#### **Assessments of fertility**

Medical documentation of oophorectomy, hysterectomy, or tubal ligation must be retained as source documents. Subsequent hormone level assessment to confirm the woman is not of child-bearing potential must also be available as source documentation in the following cases:

1. Surgical bilateral oophorectomy without a hysterectomy
2. Reported 12 months of natural (spontaneous) amenorrhea with an appropriate clinical profile.

In the absence of the above medical documentation, FSH testing is required of any female participant regardless of reported reproductive/menopausal status at screening/baseline.

#### **8.5       Additional assessments**

No additional tests will be performed on participants entered into this study.

### **8.5.1 Use of residual biological samples**

[REDACTED]

### **8.5.2 Serum Immunoglobulins**

In Cohort 1, total serum immunoglobulin IgG will be obtained 14 days, 70 days, 180 days, and 360 days after full course (second) vaccination. In Cohort 2, total serum immunoglobulin IgG will be obtained 180 days and 360 days after full course (second) vaccination. In Cohorts 4 and 6, total serum immunoglobulin IgG will be obtained  $\geq$  180 days and  $\geq$  360 days after full course (second) vaccination. If serum immunoglobulin IgG obtained is below 400mg/dl the patient will be withdrawn from the study.

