### 5.1 Inclusion criteria

Participants eligible for inclusion in Cohort 1 of this study must meet **all** of the following criteria:

1. Signed informed consent must be obtained prior to participation in the study
2. Age 18-55 years old inclusive at Screening
3. Diagnosis of relapsing MS by 2017 revised McDonald criteria
4. Must be willing to comply with the study schedule
5. Will be receiving an mRNA COVID-19 vaccine (Pfizer or Moderna vaccine) at least two weeks prior to starting ofatumumab
6. Eligible to receive and plan to be started on ofatumumab according to the approved labeling
7. Pre-ofatumumab serology with Hepatitis B testing not indicative of active or latent infection
8. Total serum immunoglobulin IgG  $\geq 400$  mg/dl at Screening

Participants eligible for inclusion in Cohort 2 of this study must meet **all** of the following criteria:

1. Signed informed consent must be obtained prior to participation in the study
2. Age 18-55 years old inclusive at Screening
3. Diagnosis of relapsing MS by 2017 revised McDonald criteria
4. Must be willing to comply with the study schedule
5. Will be receiving an mRNA COVID-19 vaccine (Pfizer or Moderna vaccine)
6. Currently on commercially prescribed ofatumumab for  $\geq 4$  weeks for the treatment of RMS
7. Pre-ofatumumab serology with Hepatitis B testing not indicative of active or latent infection
8. Total serum immunoglobulin IgG  $\geq 400$  mg/dl at Screening

Participants eligible for inclusion in Cohort 3 of this study must meet **all** of the following criteria:

1. Signed informed consent must be obtained prior to participation in the study
2. Age 18-55 years old inclusive at Screening
3. Diagnosis of relapsing MS by 2017 revised McDonald criteria

4. Must be willing to comply with the study schedule
5. Will be receiving an mRNA COVID-19 vaccine (Pfizer or Moderna vaccine)
6. Currently on commercially prescribed interferon or glatiramer acetate for  $\geq 4$  weeks for the treatment of RMS
7. Total serum immunoglobulin IgG  $\geq 400$ mg/dl at Screening

Participants eligible for inclusion in Cohort 4 of this study must meet **all** of the following criteria:

1. Signed informed consent must be obtained prior to participation in the study
2. Age 18-55 years old at Screening
3. Diagnosis of relapsing MS by 2017 revised McDonald criteria
4. Must be willing to comply with the study schedule

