## **9 Discontinuation and completion**

### **9.1 Discontinuation from study treatment and from study**

#### **9.1.1 Discontinuation from study treatment**

Discontinuation of study treatment for a participant occurs when study treatment is permanently stopped for any reason (prior to the planned completion of study drug administration, if any) and can be initiated by either the participant or the investigator.

The investigator must discontinue study treatment for a given participant if, he/she believes that continuation would negatively impact the participant's well-being.

Discontinuation from study treatment is required under the following circumstances:

- Participant/guardian decision
- Pregnancy
- Total serum immunoglobulin IgG  $<$  400mg/dl after Visit 2
- Use of prohibited treatment as per recommendations as per the USPI
- Any situation in which study participation might result in a safety risk to the participant
- Diagnosis of PML
- Participants with active serious infections or reactivation

- Skin and/or mucosal reactions which raise the suspicion of severe generalized major skin reactions (Stevens-Johnson syndrome, or toxic epidermal necrolysis-Lyell's syndrome)
- Hypersensitivity to ofatumumab
- Protocol violation that results in a significant risk to the participant's safety
- Emergence of certain adverse events, such as malignancy (except successfully treated basal cell carcinoma, *in situ* squamous cell carcinoma and *in situ* carcinoma of cervix of uterus), liver failure or serious chronic infection (such as human immunodeficiency virus (HIV))
- Severe hyperproteinemia
- Non-compliance with study drug or study procedures

If discontinuation from study treatment occurs, the investigator should make a reasonable effort to understand the primary reason for the participant's discontinuation from study treatment and record this information.

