Participants who discontinue study treatment or who decide they do not wish to participate in the study further should NOT be considered withdrawn from the study UNLESS they withdraw their consent (see [Section 9.1.2 'Withdrawal of Informed Consent' section](#)). **Where possible, they should return for the EOS Visit.** At EOS visits all dispensed study drug to participants in Cohort 1 should be reconciled and the adverse event and concomitant medications should be recorded on the CRF (for participants in both cohorts). If they fail to return for these assessments for unknown reasons, every effort (e.g. telephone, e-mail, letter) should be made to contact the participant/pre-designated contact as specified in the lost to follow-up section. This contact should preferably be done according to the study visit schedule.

If the participant cannot or is unwilling to attend any visit(s), the site staff should maintain regular telephone contact with the participant, or with a person pre-designated by the participant. This telephone contact should preferably be done according to the study visit schedule.

After discontinuation from study treatment, at a minimum, in abbreviated visits, the following data should be collected at clinic visits or via telephone/email contact:

- New / concomitant treatments
- Adverse Events / Serious Adverse Events

The investigator must also contact the IRT to register the participant's discontinuation from study treatment.

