### **9.1.2 Discontinuation from study**

Discontinuation from study is when the participant permanently stops receiving the study treatment, and further protocol-required assessments or follow-up, for any reason.

Participants must be discontinued from the study under the following circumstances:

- Failure to receive a complete COVID-19 mRNA (Pfizer or Moderna) vaccination course (2 doses)
- IgG  $\leq$  400mg/dl

If the participant agrees, a final evaluation at the time of the participant's study discontinuation should be made as detailed in the assessment table under the End of Study Visit (refer to [Section 8](#)).

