Cohort 2: Relapsing MS participants receiving a full course (2 doses) of a non-live COVID-19 mRNA vaccine ≥4 weeks after ofatumumab start.

Will continue taking their prescribed ofatumumab as per their current dosing schedule.

Cohort 3: Relapsing MS participants receiving a full course (2 doses) of a non-live COVID-19 mRNA vaccine ≥4 weeks after start of prescribed interferon or glatiramer acetate.

Will continue administration of their prescribed interferon or glatiramer acetate as per their current dosing schedule.

Cohort 4: Relapsing MS participants having completed a full course (2 doses) of a non-live COVID-19 mRNA vaccine ≥4 weeks after ofatumumab start.

Will continue taking their prescribed ofatumumab as per their current dosing schedule.

Cohort 5: Relapsing MS participants having completed a full course (2 doses) of a non-live COVID-19 mRNA vaccine ≥4 weeks after glatiramer acetate or interferon start.

Will continue taking their prescribed glatiramer acetate or interferon as per their current dosing schedule.

Cohort 6: Relapsing MS participants having completed a full course (2 doses) of a non-live COVID-19 mRNA vaccine ≥4 weeks after ofatumumab start and having received a booster ≥14 days prior to screening.

Will continue taking their prescribed ofatumumab as per their current dosing schedule.

Study completion

According to the protocol, study completion is defined as when the last participant completes the end of study (EOS) visit. Participants who discontinue study treatment or who decide they do not wish to participate in the study further should NOT be considered withdrawn from the study UNLESS they withdraw their consent. Where possible, they should return for the EOS visit.

Study design schematics for Cohorts 1, 2 and 3 are shown in Figures 1, 2, 3 and 4. Study design schematics for Cohorts 4, 5 and 6 are shown in Figures 5 and 6.

Figure 1 Study Design (Cohort 1, Pfizer)

[figure not shown]

Figure 2 Study Design (Cohort 1, Moderna)

[figure not shown]

Figure 3 Study Design (Cohorts 2 and 3, Pfizer)

[figure not shown]

Figure 4 Study Design (Cohorts 2 and 3, Moderna)

[figure not shown]

Figure 5 Study Design (Cohorts 4, 5 and 6, Pfizer)

[figure not shown]
[figure not shown]

Figure 6 Study Design (Cohorts 4, 5 and 6, Moderna)

Primary analysis time point

The primary analysis time point is Visit 4 for Cohorts 1, 2 and 3, and Visit 2 for Cohorts 4, 5 and 6.

Interim analysis

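### Low total IgG: Protocol 9.1.2 uses a different threshold from 8.5.2 and 9.1.1, and the three sections disagree on whether the participant leaves the study (minor, wrong as written)

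*Protocol*

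**What the plan says.** Entry (Protocol 5.1, all six cohorts) requires "Total serum immunoglobulin IgG $\geq 400$ mg/dl at Screening", so a value of exactly 400 is eligible.

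Three later sections act on low IgG:

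- **8.5.2**, after naming the draws for Cohorts 1, 2, 4 and 6: "If serum immunoglobulin IgG obtained is below 400mg/dl the patient will be withdrawn from the study".
- **9.1.1**, among the reasons to stop study treatment: "Total serum immunoglobulin IgG $<$ 400mg/dl after Visit 2". Its general text then says: "Participants who discontinue study treatment or who decide they do not wish to participate in the study further should NOT be considered withdrawn". This concerns study status, and withdrawal of consent is the only exception. SAP 1.1 repeats that they "should NOT be considered withdrawn from the study UNLESS they withdraw their consent". On follow-up, 9.1.1 says "Where possible, they should return for the EOS Visit" and adds "After discontinuation from study treatment, at a minimum, in abbreviated visits, the following data should be collected at clinic visits or via telephone/email contact". The list that follows contains only concomitant treatments and AEs/SAEs.
- **9.1.2** lists IgG at or below 400 mg/dl as a mandatory reason to leave the study, and defines that exit: "Discontinuation from study is when the participant permanently stops receiving the study treatment, and further protocol-required assessments or follow-up, for any reason".

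SAP 2.6.3 and 2.6.4 score a missing antibody assay as non-response for the secondary endpoints, whatever the intercurrent event. SAP 2.6.6 adds an observed-case analysis, and SAP 2.3.1 lists discontinuations with their primary reason.

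**The concern.** A site that finds IgG below 400 can follow 8.5.2 or 9.1.2 and end all assessments, or follow 9.1.1 and keep the participant under observation. Under the first reading the later antibody results do not exist, and non-response imputation (NRI) turns them into failures even if the participant was positive when last tested. A zero in the sustained-response table would then reflect a protocol instruction, not an antibody measurement, and its frequency would depend on which section the site read. Separately, a participant at exactly 400 is eligible under 5.1 and untouched by 8.5.2 and 9.1.1, yet meets a mandatory exit criterion in 9.1.2. That bullet does not carry the after-Visit-2 limit found in 9.1.1.

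**Working it through.** **Step 1. The rules side by side.**

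| Protocol section | IgG (mg/dl) | Consequence | Cohorts |
|---|---|---|---|
| 5.1 | 400 or above | eligible | all six |
| 8.5.2 | below 400 | leaves the study | paragraph names 1, 2, 4, 6 |
| 9.1.1 | below 400, after Visit 2 | treatment stops; general text keeps participant in study | no limit |
| 9.1.2 | 400 or below | leaves the study; assessments end | no limit |

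On the threshold, 9.1.2 is the outlier, and only at the single value 400. On study status, 9.1.1 is the outlier for every value below 400. Tables 8-3 to 8-6 also schedule immunoglobulin draws in Cohorts 3 and 5, which 8.5.2 does not name but 9.1.1 and 9.1.2 do not exclude.

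**Step 2. The plan's precision figure, as a yardstick.** Protocol 12.8.1 gives half-widths of 20.1%, 19% and 17.5% for n = 20 at rates of 70%, 75% and 80%. The formula 1.96 × √(p(1−p)/20) gives 20.08%, 18.98% and 17.53%, so they reproduce. Enrolment per group is 20 × 1.10 = 22.

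**Step 3. Later antibody results lost, per participant.** Inputs: visit days from Tables 8-1 to 8-6, antibody windows from SAP Tables 2, 5 and 8, and an End of Study (EOS) visit within 7 days of premature discontinuation (Protocol 8).

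| IgG draw | Day (Pfizer / Moderna) | Antibody window ends | Margin | Later time points | Lost on study exit | Lost under 9.1.1 |
|---|---|---|---|---|---|---|
| Cohort 1, 14-day | 36 / 43 | 64 / 71 | 28 days | 70, 180, 270, 360 | 4 | 0 to 4 |
| Cohort 1, 70-day | 92 / 99 | 147 / 154 | 55 days | 180, 270, 360 | 3 | 0 to 3 |
| All cohorts, 180-day | 202 / 209 | 247 / 254 | 45 days | 270, 360 | 2 | 0 to 2 |

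An early EOS sample does not fill a later time point unless the IgG result takes longer than the margin less 7 days, that is 21, 48 or 38 days. Laboratory turnaround is not stated; I assume it is shorter. Under 9.1.1 the loss is 0 if scheduled draws continue, one less than the maximum if only the EOS sample is taken on its scheduled day, and the maximum if only the minimum data are collected or EOS is brought forward. At exactly 400, 9.1.2 loses 2, 3 or 4 and the other two sections lose none.

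**Step 4. Effect on a reported rate.** One would-be responder scored as non-response costs 1/22 = 4.5 points in the cohort group and 1/88 = 1.1 points overall. One who would have turned negative costs nothing. Base rates below are assumed; intervals are exact 95%.

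| Would-be responders lost | From 15/22 (68.2%) | From 18/22 (81.8%) |
|---|---|---|
| 0 | 68.2% (45.1 to 86.1) | 81.8% (59.7 to 94.8) |
| 1, NRI | 14/22 = 63.6% (40.7 to 82.8) | 17/22 = 77.3% (54.6 to 92.2) |
| 1, observed case | 14/21 = 66.7% | 17/21 = 81.0% |
| 3, NRI | 12/22 = 54.5% (32.2 to 75.6) | 15/22 = 68.2% (45.1 to 86.1) |

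The range of 0 to 3 cases is an assumption; the documents give no rate of low IgG.

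**Step 5. Which endpoints.** The primary time point is Visit 4 in Cohorts 1 to 3 and Visit 2 in Cohorts 4 to 6 (SAP 1.1). After screening, IgG is first drawn at Visit 4 in Cohort 1, together with the primary antibody sample, and at the 180-day visit elsewhere. The primary sample is therefore normally already taken. Sustained response at later visits is exposed. Immune conversion (SAP 2.6.1) counts any qualifying time point, so it can be affected only where conversion had not yet been shown at exit.

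**The case against.** The strongest reply is that 9.1.1 and 9.1.2 can apply together: low IgG stops treatment and also requires exit. Both places that attach a study status specifically to low IgG say leave; only a general sentence in 9.1.1, which does not mention IgG, says otherwise. On that view the repair is one symbol in 9.1.2 and an exception clause in 9.1.1. This stands in part: it is a legitimate way to remove the contradiction. It does not show that the present text is consistent, because 9.1.1 admits withdrawn consent as its only exception and no precedence is given. It would also keep producing missing results that are scored as failures.

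Three further points stand. Draws after a permanent stop are off treatment, possibly on another therapy, while the objective concerns ofatumumab-treated participants. Table 6-2 requires study discontinuation for other MS disease-modifying therapy, and 6.2.2 words the ban as combination with study drug, so the effect of a switch after stopping is unclear. And the SAP amendment is dated 28-Jun-2023, before database lock; the documents do not show whether any draws remain to be saved.

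A reader might infer that all three sections disagree on the threshold, or that the problem is confined to Cohorts 1, 2, 4 and 6. Neither is supported: 8.5.2 and 9.1.1 agree on below 400, and the 9.1.1 and 9.1.2 bullets carry no cohort limit. Nor does 9.1.1 drop antibody sampling altogether, since it asks for an EOS visit where possible and that visit includes a SARS-CoV-2 antibody draw.

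**Conclusion.** The text is wrong as written on two points, and the fault is minor. The 9.1.2 threshold contradicts the entry criterion at one value. The study status for IgG below 400 is contradictory, with no rule of precedence.

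The cost is up to 2, 3 or 4 later antibody results per affected participant, depending on the draw, and 4.5 points of NRI rate in a cohort group for each lost would-be responder. One such case is small beside the planned half-width of 17.5 to 20.1 points. This rests on three assumptions: at least one participant falls to the threshold, the site follows the exit rule, and laboratory turnaround is short enough that an early EOS sample stays in the current window. With no low IgG the effect is nil.

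A reader might infer that the primary response rate is biased. The documents do not support that. The primary sample precedes or coincides with the first post-screening IgG draw in every cohort. The one exception is a value of exactly 400 at Screening, if 9.1.2 were applied literally before the primary sample. No hypothesis is tested, and the observed-case analysis and the listing of discontinuation reasons already show part of the effect, though neither recovers samples nor aligns sites.

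**What to change.** 1. In Protocol 9.1.2, change the IgG bullet to below 400 mg/dl.
2. State one consequence in 8.5.2, 9.1.1 and 9.1.2. I would stop study treatment, keep the participant in the study and continue the scheduled SARS-CoV-2 antibody draws. Name those draws in the 9.1.1 minimum data set; aligning the thresholds alone would not secure them.
3. Say whether the rule covers Cohorts 3 and 5, whose interferon or glatiramer acetate is commercially prescribed, and how it fits with Table 6-2 if the participant switches MS therapy.
4. Flag antibody results after the stop as off treatment in the listings. The imputation rule need not change: NRI applies only to missing assays, so an observed result is used as observed.

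The cost is a short protocol amendment with the approvals in Protocol 14.1, at up to 30 centers, and a few off-treatment samples. It adds no visit, draw or analysis. If follow-up is already complete, report instead how many participants left for low IgG, at which visit, and their last antibody result.

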### **8.5.3 Bio-banked samples**

As new and relevant assays are validated during this study and after its completion, (1) whole blood and (1) serum sample will be collected at Screening and Visit 4 for Cohorts 1, 2 and 3 to be bio-banked for yet to be identified analyses. For Cohorts 4, 5, and 6, (1) whole blood and (1) serum sample will be collected at Screening Visit/Visit 1 only.

## **9 Discontinuation and completion**

### **9.1 Discontinuation from study treatment and from study**

#### **9.1.1 Discontinuation from study treatment**

Discontinuation of study treatment for a participant occurs when study treatment is permanently stopped for any reason (prior to the planned completion of study drug administration, if any) and can be initiated by either the participant or the investigator.

The investigator must discontinue study treatment for a given participant if, he/she believes that continuation would negatively impact the participant's well-being.

Discontinuation from study treatment is required under the following circumstances:

- Participant/guardian decision
- Pregnancy
- Total serum immunoglobulin IgG  $<$  400mg/dl after Visit 2
- Use of prohibited treatment as per recommendations as per the USPI
- Any situation in which study participation might result in a safety risk to the participant
- Diagnosis of PML
- Participants with active serious infections or reactivation

- Skin and/or mucosal reactions which raise the suspicion of severe generalized major skin reactions (Stevens-Johnson syndrome, or toxic epidermal necrolysis-Lyell's syndrome)
- Hypersensitivity to ofatumumab
- Protocol violation that results in a significant risk to the participant's safety
- Emergence of certain adverse events, such as malignancy (except successfully treated basal cell carcinoma, *in situ* squamous cell carcinoma and *in situ* carcinoma of cervix of uterus), liver failure or serious chronic infection (such as human immunodeficiency virus (HIV))
- Severe hyperproteinemia
- Non-compliance with study drug or study procedures

If discontinuation from study treatment occurs, the investigator should make a reasonable effort to understand the primary reason for the participant's discontinuation from study treatment and record this information.

Participants who discontinue study treatment or who decide they do not wish to participate in the study further should NOT be considered withdrawn from the study UNLESS they withdraw their consent (see [Section 9.1.2 'Withdrawal of Informed Consent' section](#)). **Where possible, they should return for the EOS Visit.** At EOS visits all dispensed study drug to participants in Cohort 1 should be reconciled and the adverse event and concomitant medications should be recorded on the CRF (for participants in both cohorts). If they fail to return for these assessments for unknown reasons, every effort (e.g. telephone, e-mail, letter) should be made to contact the participant/pre-designated contact as specified in the lost to follow-up section. This contact should preferably be done according to the study visit schedule.

If the participant cannot or is unwilling to attend any visit(s), the site staff should maintain regular telephone contact with the participant, or with a person pre-designated by the participant. This telephone contact should preferably be done according to the study visit schedule.

After discontinuation from study treatment, at a minimum, in abbreviated visits, the following data should be collected at clinic visits or via telephone/email contact:

- New / concomitant treatments
- Adverse Events / Serious Adverse Events

The investigator must also contact the IRT to register the participant's discontinuation from study treatment.

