## 8 Visit schedule and assessments

The below Assessment Schedules ([Table 8-1](#), [Table 8-2](#), [Table 8-3](#), [Table 8-4](#), [Table 8-5](#) and [Table 8-6](#)) list all assessments with an X when they are performed. All data obtained from these assessments must be supported in the participant's source documentation. The "X" in the table denotes the assessments to be recorded in the clinical database or received electronically from a vendor. The "S" in the table denotes the assessments that are only in the participant's source documentation and do not need to be recorded in the clinical database.

Participants should be seen for all visits/assessments as outlined in the assessment schedules or as close to the designated day/time as possible. The Investigator should promote compliance by instructing the participant to attend the study visits as scheduled and by stating that compliance is necessary for the participant's safety and the validity of the study. Missed or rescheduled visits should not lead to automatic discontinuation. The participant should be instructed to contact the Investigator if he/she is unable for any reason to attend a study visit as scheduled or if he/she is unable for any reason to take the study treatment as prescribed.

Participants who prematurely discontinue the study should be scheduled for the End of Study (EOS) visit within 7 days. At this final visit, all the assessments mentioned under EOS visit should be performed, all dispensed investigational product should be reconciled, and the

adverse event and concomitant medications recorded on the CRF. Participants that prematurely discontinue should also have a remote follow-up safety visit performed 30 days after the EOS visit.

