2.1.1 General definitions

Treatment of interest

The treatment of interest will refer to the administration of a COVID-19 mRNA vaccine (either Pfizer or Moderna) to participants in each of the 6 cohorts. Participants will obtain a COVID-19 mRNA vaccine from their HCP (private insurance) or appropriate federal, state or local program.

Additional treatment

- Ofatumumab provided by Novartis in an auto-injector containing 20 mg s.c. ofatumumab (20 mg/0.4ml) for s.c. administration to participants in **Cohort 1** as per the assessment schedule.
- Commercially prescribed ofatumumab treatment for participants in **Cohort 2** as per their current dosing schedule.

- Commercially prescribed interferon or glatiramer acetate treatment for participants in **Cohort 3** as per their current dosing schedule.
- Commercially prescribed ofatumumab treatment for participants in **Cohort 4** as per their current dosing schedule.
- Commercially prescribed interferon or glatiramer acetate treatment for participants in **Cohort 5** as per their current dosing schedule.
- Commercially prescribed ofatumumab treatment for participants in **Cohort 6** as per their current dosing schedule

Study day, onset day, and event duration

The **study day** of an assessment will be derived relative to the date of Visit 2 (Study Day 1), primarily for use in the derivation of analysis visits using visit windows (see [Section 2.4.1.1](#)).

For data including but not limited to adverse events, medications, medical history, non-drug therapies/procedures and MS relapses, the **onset day** will be derived relative to the date of Visit 1 (Screening) as described below.

For event dates on or after the date of Visit 1, the day of the event will be calculated as follows:

- (date of event – date of Visit 1) + 1

For event dates prior to the date of Visit 1, the day of the event will be calculated as follows:

- (date of event – date of Visit 1)

The **duration of an event** in days will be calculated as follows:

- (event end date – event start date) + 1

Screening

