2.5.3 Handling of intercurrent events

Non-response imputation (NRI) approach will be applied to missing post-vaccination antibody assay regardless of intercurrent events.

NRI is a conservative imputation method for dichotomous variables. NRI assumes that a participant is a treatment failure if the participant discontinues the study prematurely. Hence, for missing data the primary endpoint will be imputed as “No”. Refer to [Section 5.1.3.3](#).

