2.6.3 Handling of intercurrent events

NRI approach will be applied to missing antibody assay regardless of intercurrent events.

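### Participants who stop their MS drug but stay in the study need not have further antibody assays, and the resulting gaps are scored as vaccine non-response, mainly in the secondary endpoints

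*Protocol*

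**What the plan says.** Protocol 9.1.1 does not treat a participant who stops study treatment as withdrawn unless consent is withdrawn. For later contact, whether in clinic or by telephone or email, it states "After discontinuation from study treatment, at a minimum, in abbreviated visits, the following data should be collected". The list that follows has two items: new or concomitant treatments, and adverse events. On the closing visit it says "Where possible, they should return for the EOS Visit", without saying when that visit falls for someone who has stopped treatment only.

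The glossary counts control and background therapy as study treatment, and Table 6-1 names ofatumumab, interferon and glatiramer acetate, so the rule reaches all six cohorts. The treatment under study is something else. SAP 2.1.1 says "The treatment of interest will refer to the administration of a COVID-19 mRNA vaccine".

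For the primary endpoint, SAP 2.5.3 says "Non-response imputation (NRI) approach will be applied to missing post-vaccination antibody assay regardless of intercurrent events". For the secondary endpoints, SAP 2.6.3 says "NRI approach will be applied to missing antibody assay regardless of intercurrent events". Protocol 12.4.3 and 12.4.4 give the same rule for the primary endpoint. An observed-case analysis is planned as a supplement (Protocol 12.4.6, SAP 2.5.6 and 2.6.6).

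**The concern.** Stopping ofatumumab, interferon or glatiramer acetate after vaccination does not make the antibody result unmeasurable. Under 9.1.1, however, a site can comply in full by telephone or email and collect no endpoint data after the stop. Non-response imputation (NRI) then fills each gap.

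Sustained response at the later visits thus becomes a mixture of losing antibody and stopping an MS drug. Some reasons for stopping, such as hypersensitivity to ofatumumab, apply to one drug only, so imputed failures need not fall evenly across the cohort groups that will be read side by side. The observed-case supplement leaves these participants out and cannot recover what their results would have been.

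**Working it through.** **Which endpoints are exposed.** SAP 1.1 fixes the primary sample: "The primary analysis time point is Visit 4 for Cohorts 1, 2 and 3, and Visit 2 for Cohorts 4, 5 and 6". Setting this beside the schedules and the SAP windows gives:

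- Cohort 1, primary: not exposed. The first ofatumumab dose is given at Visit 4, after that visit's assessments (Protocol 6.3.2), so the primary sample precedes any stop of ofatumumab.
- Cohorts 4, 5 and 6, primary: not exposed to a later stop. The sample is taken on Day 1.
- Cohorts 2 and 3, primary: exposed only to a stop between enrolment and Visit 4 (Day 36 Pfizer, Day 43 Moderna). Even then, an EOS sample taken after dose 2 and up to Day 119 (Pfizer) or Day 126 (Moderna) falls in the 14-day window of SAP Table 5. These limits are the midpoints (36 + 202)/2 = 119 and (43 + 209)/2 = 126.
- Sustained response: exposed in every cohort, from Day 92/99 in Cohort 1 and from Day 202/209 in the others.
- Immune conversion in Cohorts 4 and 5: exposed, because SAP 2.6.1 needs a positive assay after Visit 2. One later sample would be enough; with none, the participant is scored as not converting.

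**Why one EOS sample does not fill the gap.** Suppose a Cohort 2 Pfizer participant stops and has the EOS visit on Day 105. That sample maps to the 14-day window. The 180-, 270- and 360-day results remain missing, and all three are scored as non-response.

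**The plan's own figures.** Inputs from Protocol 12.8.1: n = 20, response rates 70%, 75% and 80%, 22 enrolled per cohort group. The half-width 1.96 × √(p(1 − p)/20) gives 20.1, 19.0 and 17.5 points, matching the stated values. The enrolment figure is 20 × 1.1 = 22.

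**Size of the effect.** Let m of 22 participants have no assay at a time point, with missingness unrelated to antibody status. The expected scored rate is p(22 − m)/22, a loss of pm/22.

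- m = 1: 0.70/22 = 3.2 points; 0.75/22 = 3.4; 0.80/22 = 3.6.
- m = 2: 6.4, 6.8 and 7.3 points, giving scored rates of 63.6%, 68.2% and 72.7%.
- m = 4: 12.7, 13.6 and 14.5 points.
- m = 0 (assay still drawn after the stop): no loss.

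The documents do not give m, so the range of 3.2 to 14.5 points for m = 1 to 4 is an assumption. The 70% to 80% rates are planning values for the primary endpoint; no rates are given for the late visits, where most of the exposure lies.

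**The case against.** The 9.1.1 list is a floor, written to cover contact by telephone or email, and nothing tells a site to stop sampling a participant who still attends. Section 8 asks that participants be seen for all scheduled visits. For those leaving the study early it adds "At this final visit, all the assessments mentioned under EOS visit should be performed", and the schedules mark the antibody assay at EOS. A reader might infer that any stop leaves the outcome missing; the documents do not support that. A stop can leave it missing. What remains is that a site can meet the minimum without drawing a sample, and that a single EOS sample, requested only where possible, cannot serve several later time points.

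A reader might also take the planned 10% drop-out as the rate of affected participants. It is not. It counts drop-outs, not people who stop a drug and stay, and those who leave the study or withdraw consent would not be recovered by any change to 9.1.1. Participants discontinued under 9.1.2, for low IgG or an incomplete vaccine course, are likewise outside the point.

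The analysis is also descriptive: proportions with exact intervals, no hypothesis tests, and NRI openly described as conservative. That limits the consequence, but the scored proportions are still what will be reported. Finally, NRI already applies only where an assay is missing. No rule turns a collected post-stop result into a failure, so the weakness lies in data collection and not in the SAP rule.

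**Conclusion.** The point stands in limited form. The minimum data set omits the one measurement on which the immune endpoints rest, so stopping an MS drug can be recorded as vaccine non-response. It bears mainly on sustained response in all cohorts and on conversion in Cohorts 4 and 5. A general threat to the primary endpoint, which a reader might infer, is not supported: it is exposed only for stops before Visit 4 in Cohorts 2 and 3, and partly protected there by the width of the 14-day window. Nor do the documents show that the comparison between groups is distorted. They allow it, but give no stopping rates by group.

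The effect per missing participant rests on a group of 22, the primary-endpoint planning rates, and missingness unrelated to antibody status. How many participants would be affected is unknown. This is a worthwhile, inexpensive improvement to data collection.

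**What to change.** In Protocol 9.1.1, add the SARS-CoV-2 antibody assay at each remaining scheduled sampling visit to the minimum data set. Apply it to participants who stop study treatment but have neither withdrawn consent nor been discontinued from the study under 9.1.2. Samples can be taken at the site, or remotely where Section 3 allows. State also when the EOS visit takes place for participants who have stopped treatment only.

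The existing SAP rule then uses these assays as observed, so no change to NRI is needed; a flag for assays taken after a stop is optional.

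The cost is a protocol amendment with IRB approval and a few more blood draws after stopping, which participants may decline. Home collection should not be assumed for everyone: Section 4.5 describes the planned home visits as Cohort 1 only, with other home nursing considered case by case.
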